6.3. Analyses of Exploratory Efficacy Endpoints

For subjects with baseline proteinuria above the upper limit of normal (ULN), the proportion of subjects achieving at least a 50% reduction in proteinuria over time, and the proportion of subjects achieving complete clinical remission of proteinuria (defined as normalization of proteinuria, which is <200 mg/g) at Week 12 and Week 52, will be tabulated. Changes and percentage changes from baseline in proteinuria will be summarized over time. Since proteinuria will be assessed in two separate ways (one using the mean of the triplicate first-morning spot urine, the other using the 24-hour urine collection), there will be two sets of tables for the proteinuria summaries described in this paragraph. In addition, changes and percentage changes from baseline in proteinuria will also be summarized descriptively based on the subgroup of baseline uPCR < 1000 mg/g vs. baseline uPCR \geq 1000 mg/g.

Additional key biopsy features, including glomerular leukocyte infiltration (Total #, percentage, score), glomerular macrophage infiltration as measured by CD 68 staining, glomerular crescents (total #, percentage, score), Mesangial hypercellularity (total #, percentage, score), Deposits by electron microscopy (absent/present, characters of deposits, locations of deposits, degree of foot process effacement), and C3G histologic index (activity score, chronicity score), will be summarized and listed. Changes over time will also be summarized for the numeric biopsy features.

Ophthalmologic features including change in maximum drusen size (measured by total volume of drusen) at baseline and Week 52, and change in number of intermediate or large drusen at Week 52, will be summarized for subjects who have both baseline and on-study ophthalmologic evaluations and listed. In situations where no subjects had on-study ophthalmologic evaluations, outputs will still be generated for those baseline evaluations. Summaries will further be separated by left eye and right eye, respectively.

7. SAFETY ANALYSIS

7.1. Adverse Events

Treatment-emergent adverse events (TEAEs) are defined as those AEs that develop or worsen after the first dose of study medication (or after randomization in Group 2) and up to 56 days beyond the last dose of study medication. Analysis of AEs (as discussed below) will be limited to TEAEs, but data listings will include all AEs regardless of their timing.

All reported AEs will be coded using the current version of MedDRA and summarized by System Organ Class (SOC) and Preferred Term (PT). All summaries by SOC and PT will be ordered by decreasing frequency of subjects within each SOC and then similarly by decreasing frequency of subjects within each PT. In the case of equal frequency of number of subjects in SOC or PTs, summaries of TEAEs will be sorted alphabetically. Rules for handling missing severity, relationship to study drug, relationship to infusion procedure, outcome, and missing dates of AEs are described in Section 13.

If a PT was reported more than once for the same subject, that subject would only be counted once in the incidence for that PT. For subjects experiencing the same PT at multiple severities, the occurrence of the AEs with the greatest severity will be used in the analysis of incidence by severity. For subjects experiencing the same PT at multiple relationship levels, the occurrence of the AEs with the strongest relationship to study drug will be used in the analysis of incidence by relationship to study drug.

The AE summaries will be presented by treatment group and overall. The number and incidence of rejection episodes and graft loss will also be summarized.

An overall summary for TEAEs including number of subjects who experience a TEAE, number of total TEAEs and number of unique TEAEs will be provided:

- TEAE
- Treatment-related TEAE
 - Related
 - Not related
- Infusion-related TEAEs
 - Related
 - Not related
- Serious TEAE
- Maximum severity of TEAEs
- Infusion site reaction (yes/no)
- TEAE leading to treatment discontinuation
- TEAE leading to dose interruption
- TEAE leading to study discontinuation
- TEAE leading to death

The following summaries will be provided:

- TEAEs by SOC and PT
- TEAEs by PT in decreasing order of frequency
- Treatment-related TEAEs by SOC and PT
- Infusion-related TEAEs by SOC and PT
- Serious TEAEs by SOC and PT
- TEAE by SOC, PT and maximum severity
- TEAE leading to treatment discontinuation by SOC and PT
- TEAE leading to dose interruption by SOC and PT
- TEAE leading to study discontinuation by SOC and PT
- TEAE leading to death by SOC and PT

The following listings will be provided:

- All AEs
- Serious Adverse Events (SAEs)
- AEs leading to study drug discontinuation
- Death
- Treatment-related Adverse Events
- Infusion-related Adverse Events

7.2. Clinical Laboratory Data

All laboratory results will be standardized by converting values in original units to values in standard units and classified as normal, abnormal low, or abnormal high on normal ranges supplied by the local laboratories and upon employing standardization.

When a certified local laboratory is used instead of a central laboratory due to COVID-19 pandemic, the units and normal ranges might be different. Therefore, all local laboratory values will be standardized to a central laboratory value using the following formula:

$$X_S = L_S + \frac{U_S - L_S}{U_X - L_X} \times (X - L_X)$$

Where,

X : local lab value

X_S : standardized value of X

L_S : Low normal range for central lab

U_S : High normal range for central lab

L_X : Low normal range for local lab

U_X : High normal range for local lab

Specifications will be developed to detail all the steps necessary for developing the standardized laboratory values and to address issues like missing normal ranges or negative standardized laboratory values.

Observed and change from baseline of clinical laboratory data (hematology, serum chemistry, coagulation and continuous urinalysis parameters) will be summarized at each analysis visit by treatment group and overall. Categorical urinalysis data will also be tabulated at each analysis visit when applicable.

In addition, liver abnormalities will be summarized at each analysis visit including following variables by treatment group and overall:

- ALT or AST $\geq 3 \times \text{ULN}$
- ALT or AST $\geq 3 \times \text{ULN}$ and (TBL $> 2 \times \text{ULN}$ or INR > 1.5)
- ALT or AST $\geq 5 \times \text{ULN}$
- ALT or AST $> 8 \times \text{ULN}$

Clinical laboratory test values are potentially clinically significant (PCS) if they meet either the low or high PCS criteria listed in the table below:

Table 1: Criteria for Potentially Clinically Significant Laboratory Tests

Parameter	Criteria
Hematology	
WBC (total) ($\times 10^9/\text{L}$)	< 3.0 > 16
Lymphocyte ($\times 10^9/\text{L}$)	< 0.5 < 0.8 > 12
Neutrophils ($\times 10^9/\text{L}$)	< 1.0 < 1.5 > 12
RBC ($\times 10^{12}/\text{L}$)	< 3.3 > 6.8
Hemoglobin (g/dL)	< 10
Platelet count ($\times 10^9/\text{L}$)	< 100 > 600

Table 1: Criteria for Potentially Clinically Significant Laboratory Tests

Parameter	Criteria
Serum Chemistry	
ALT	> 1.5xULN > 3.0xULN
AST	> 1.5xULN > 3.0xULN
ALP	> 1.5xULN > 3.0xULN
Total Serum Bilirubin	> 1.5xULN
GGT	> 3.0xULN
ALT or AST > 3xULN and concurrent elevated total bilirubin defined as	> 2.0xULN

For the following serum chemistry parameters: Creatinine; estimated Glomerular Filtration Rate (using CKD-EPI formula) –screening only; Albumin; LDH; Creatine kinase (CK); Uric acid; Glucose; Sodium; Potassium; and Chloride, abnormal values will be used as potentially clinically significant.

Similarly, for Urinalysis parameters, Protein; Glucose; Blood; Nitrite; and Leukocyte esterase, abnormal values will be used as potentially clinically significant.

The number and percentage of subjects with post-baseline PCS laboratory values will be tabulated by treatment group and overall. A listing of subject data with at least one post-baseline PCS value will be provided.

All laboratory values will be listed for each subject.

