#### 6.2. Study Design

This is an open-label, randomized, controlled, Phase 2 study consisting of a single cohort of up to 12 subjects with clinical and pathologic evidence of recurrent C3G or IC-MPGN in a renal allograft. Subjects will be randomized 3:1 to Group 1 (pegcetacoplan treatment throughout the main period) or Group 2 (no pegcetacoplan treatment for the first 12 weeks of the main period, followed by pegcetacoplan treatment), respectively. The visit schedule will be the same, regardless of randomization.

Pathologic evidence of disease recurrence requires a biopsy-based diagnosis of C3G or IC-MPGN in the renal allograft, confirmed by a study pathologist. The diagnosis need not be the same in the native kidney and the renal allograft; for example, a subject with C3G in the native kidney and IC-MPGN post transplant is still eligible for the study.

Subjects with either preexisting disease recurrence or upon initial identification of clinical and pathologic recurrence of disease will be invited to enter screening. Subjects must also have an eGFR of at least 15 mL/min/1.73 m^2 and no more than 50% fibrosis on renal biopsy.

The study will require a total of 3 renal allograft biopsies, during screening, Week 12, and Week 52. Flexibility has been built in for each biopsy as described below:

- Screening renal allograft biopsy: must occur within 4 weeks leading up to the day of randomization
  - A nonstudy biopsy may be used as the baseline biopsy provided it meets the following criteria:
    - it was performed no more than 12 weeks prior to Week 1
    - the subject has remained clinically stable since the biopsy with no changes in medication regimens that would be expected to significantly alter the baseline biopsy findings

- the prior biopsy is available for central pathology review and includes all the required components of a study baseline biopsy (see Section 10.9 for more details)
- Week 12 renal allograft biopsy: must occur at a time point between Weeks 12 and 14, inclusive; Group 2 subjects cannot begin pegcetacoplan administration until after the biopsy occurs
- Week 52 renal allograft biopsy: must occur at a time point between Weeks 48 and 52, inclusive, but after completion of the 24-hour urine collection scheduled for Week 48.

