Abbreviations: ACR = albumin-to-creatinine ratio; AH50 = 50% alternative hemolytic complement pathway activity, ALP = alkaline phosphatase; ALT = alanine aminotransferase; aPTT = activated partial thromboplastin time; AST = aspartate aminotransferase; BUN = blood urea nitrogen; CH50 = 50% classical hemolytic complement pathway activity, CKD-EPI = Chronic Kidney Disease-Epidemiology Collaboration; FSH = follicle-stimulating hormone; GGT = γ-glutamyltransferase; Hb = hemoglobin; HbcAb = hepatitis B core antibody; HbsAg = hepatitis B surface antigen; HCV = hepatitis C; HDL = high-density lipoproteins; Hib = Haemophilus influenzae type B vaccine; HIV = human immunodeficiency virus; INR = international normalized ratio; LDH = lactate dehydrogenase; LDL = low-density lipoproteins; PCR = protein-to-creatinine ratio; PCV13 = pneumococcal conjugate vaccine; PPSV23 = pneumococcal polysaccharide vaccine 23; RBC = red blood cell; WBC = white blood cell.

- A. The use of silica reagents in coagulation panels should be avoided in subjects treated with pegcetacoplan.
- B. Serum samples will only be analyzed in the event that the subject has a positive infection for Streptococcus pneumoniae, Neisseria meningitidis, or Haemophilus influenzae.

Blood and urine samples will be analyzed at a central laboratory facility. Urine samples will be analyzed by dipstick and a microscopic analysis. All laboratory reports must be reviewed, signed, and dated by the investigator. A legible copy of all reports must be filed with the subject's medical record (source document) for that visit. Any laboratory test result considered by the investigator to be clinically significant should be considered an AE (clinically significant AEs include those that require an intervention). Clinically significant abnormal values occurring during the study will be followed up until repeat test results return to normal, stabilize, or are no longer clinically significant.

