6.2. Analyses of Secondary Efficacy Endpoints

The proportion of subjects with reduction in C3c staining on renal biopsy at Week 52, change from baseline biopsy in C3c staining over time, the proportion of subjects with stabilization or improvement in eGFR or serum creatinine concentration over time, change and percentage change from baseline in eGFR and serum creatinine concentration over time, are the secondary efficacy endpoints.

The proportion of subjects with reduction in C3c staining on renal biopsy at Week 52 will be tabulated. The strategies to handle intercurrent events are same as for the primary endpoint by using composite strategy and treatment policy strategy. Changes from baseline biopsy in C3c staining over time will be summarized. A spaghetti plot of C3c staining throughout the study will be provided.

The proportion of subjects with stabilization or improvement in eGFR (defined as no more than a 25% decrease relative to baseline) over time will be tabulated. The Chronic Kidney Disease–Epidemiology Collaboration (CKD-EPI) creatinine equation for adults will be used to calculate eGFR. Changes and percentage changes from baseline in eGFR will be summarized over time.

The proportion of subjects with stabilization or improvement in serum creatinine concentration (defined as no increase or an increase of no more than 25% from baseline) over time will be tabulated. Changes and percentage changes from baseline in serum creatinine concentration will be summarized over time.

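### SAP 7.2's range-rescaling of COVID-19 local laboratory values can distort high creatinine and ULN multiples, and SAP 6.2 does not keep rescaled creatinine out of the two 25% stability endpoints

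*SAP*

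**What the plan says.** Central analysis is the default. Protocol 10.13: "Blood and urine samples will be analyzed at a central laboratory facility".

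SAP 7.2 first converts all results to standard units. It then adds a contingency, introduced by "When a certified local laboratory is used instead of a central laboratory due to COVID-19 pandemic". Because "the units and normal ranges might be different", it directs that "all local laboratory values will be standardized to a central laboratory value using the following formula". The formula maps the local normal range linearly onto the central one. No analyte is exempt, and creatinine is listed under serum chemistry in Protocol Table 3. A later specification is promised for problems such as missing ranges or negative results; values far above range are not mentioned. The same section tabulates ALT or AST at 3, 5 and 8 times the ULN.

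SAP 6.2 has two secondary responder endpoints built on creatinine. Stable or improved serum creatinine is "defined as no increase or an increase of no more than 25% from baseline"; stable or improved eGFR is "defined as no more than a 25% decrease relative to baseline", and the CKD-EPI "creatinine equation for adults will be used to calculate eGFR". Changes and percentage changes in both are also summarized. SAP 6.2 does not say whether a local creatinine enters raw or rescaled.

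On the population, Protocol 6.2: "Subjects must also have an eGFR of at least 15" (mL/min/1.73 m²).

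**The concern.** Rescaling by reference range is tolerable for values inside or near the range. These patients may have creatinine several times the upper limit, where the formula extrapolates. Reference limits differ between laboratories for reasons other than assay calibration. If both laboratories would report the same number for the same sample, the unit conversion already required by SAP 7.2 is enough, and the second step only adds error.

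At stake are the creatinine and eGFR stability tables, the matching change summaries, and the liver-abnormality tables. A subject whose creatinine rose modestly could be counted as worsened, or one who worsened as stable, because one visit used a local laboratory. The groups are planned at up to 9 and up to 3 subjects, so one such subject shows in the percentage. The primary endpoint rests on biopsy staining and is not touched.

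**Working it through.** The documents give no figure for the size of this effect, so there is none to reproduce. The formula itself can be evaluated.

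**From the documents.** X_S = L_S + s(X − L_X), with s = (U_S − L_S)/(U_X − L_X), where S is central and X local (SAP 7.2); the 25% limits (SAP 6.2); the eGFR floor of 15 (Protocol 6.2); groups of up to 9 and 3 (SAP 3).

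**Assumed.** Creatinine lower limit 0.5 to 0.7 and upper limit 1.1 to 1.3 mg/dL, in steps of 0.1: 9 ranges, hence 9 × 8 = 72 ordered local-central pairs. Creatinine of 3.0 mg/dL as the main case. Both laboratories would report the same true value.

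**Relative error.** X_S/X − 1 = (s − 1) + (L_S − s·L_X)/X. At X = L_X the formula returns L_S, and at X = U_X it returns U_S. As X rises the second term vanishes, leaving s − 1.

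| Local range | Central range | s | X_S for X = 3.0 | Shift |
|---|---|---|---|---|
| 0.7–1.3 | 0.6–1.2 | 1.00 | 0.6 + 1.00 × 2.3 = 2.90 | −3.3% |
| 0.7–1.2 | 0.6–1.2 | 1.20 | 0.6 + 1.20 × 2.3 = 3.36 | +12.0% |
| 0.7–1.1 | 0.7–1.2 | 1.25 | 0.7 + 1.25 × 2.3 = 3.575 | +19.2% |
| 0.7–1.2 | 0.7–1.1 | 0.80 | 0.7 + 0.80 × 2.3 = 2.54 | −15.3% |
| 0.7–1.2 | 0.6–1.3 | 1.40 | 0.6 + 1.40 × 2.3 = 3.82 | +27.3% |
| 0.6–1.1 | 0.6–1.3 | 1.40 | 0.6 + 1.40 × 2.4 = 3.96 | +32.0% |
| 0.6–1.3 | 0.6–1.1 | 0.714 | 0.6 + 0.714 × 2.4 = 2.31 | −22.9% |

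**Over the grid at 3.0 mg/dL.**
- One limit differs by 0.1 (24 pairs): −15.3% to +19.2%; none reaches 25%. The span is −10.7% to +13.3% at 1.5 mg/dL and −16.5% to +20.6% at 4.0.
- Each limit differs by at most 0.1 (40 pairs): −23.3% to +35.0%; 3 reach 25%.
- All 72 pairs: −35% to +70%, median absolute shift 15%; 17 reach 25%.

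**Effect on the 25% creatinine rule** (central baseline 3.0, local follow-up).
- Local 0.7–1.2, central 0.6–1.2, true rise 12% to 3.36: 0.6 + 1.2 × 2.66 = 3.79, which reads +26.4% and is classed as not stable.
- Local 0.6–1.3, central 0.6–1.2 (s = 0.857), true rise 30% to 3.90: 0.6 + 0.857 × 3.3 = 3.43, which reads +14.3% and is classed as stable.
- Both values rescaled from the same local laboratory: over the range pairs tried, with a baseline of 2.5 or 3.0, a true +25% reads as about +22% to +30%. Most of the distortion cancels.

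**Effect on eGFR.** Assume that eGFR varies as creatinine to the power −1.2. A 12% upward creatinine error gives 1.12^−1.2 = 0.873, a 12.7% fall. Error alone crosses the eGFR limit at a creatinine factor of 0.75^(−1/1.2) = 1.27; the factor is 1.33 for an exponent of −1.0 and 1.23 for −1.4.

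**ULN multiples.** Assume ALT ranges of 0–40 (local) and 10–40 (central). Local ALT of 120 is 3.0 × ULN; 10 + (30/40) × 120 = 100, or 2.5 × ULN, and the subject leaves the 3 × ULN row. Swap the laboratories and 100 (2.5 ×) becomes (40/30) × 90 = 120 (3.0 ×).

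**Weight of one subject.** 1/9 = 11 points; 1/3 = 33 points.

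**The case against.** The strongest reply is about scope. The rule is a COVID-19 contingency, and nothing in the documents shows that any creatinine was measured locally. The COVID-19 appendix cited in Protocol 4.4.1 is not in the text available, so its laboratory provisions could not be checked. The rule also sits in the safety section, and SAP 6.2 does not refer to it. All of this stands. A reader might infer that creatinine is routinely rescaled, or that rescaled values are known to feed the efficacy tables. The documents support neither. They support only that the rule's wording covers every local value and that SAP 6.2 sets no other rule for local creatinine.

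On size, the ranges are assumed, and small differences in one limit stay under 25%. That stands too. But an error need not reach 25% by itself, because it multiplies whatever true change is present, as the 12% example shows.

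On consequence, the analysis is descriptive, the endpoints are tabulated by visit, and all laboratory values are listed. A single local follow-up value therefore affects one cell. A local baseline would carry into every later comparison.

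The promised specification is open-ended and could add exemptions. The issues it names do not include values far above range, and the formula as stated has none.

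On the liver tables, SAP 7.2 refers both to local normal ranges and to standardization, so which ULN applies is unclear rather than plainly wrong. It still needs settling.

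**Conclusion.** The point holds as a conditional one. If COVID-19 local values exist and are mixed with central values within a subject, the SAP 7.2 formula can shift creatinine of 3.0 mg/dL by about 3% (equal widths, limits 0.1 apart), by up to about 15% down or 19% up (one limit 0.1 apart), and by 25% or more only when range widths differ by roughly a quarter or more. These sizes rest on assumed reference ranges and on the two laboratories agreeing on the true value. A reader might conclude that the formula generally distorts creatinine by as much as the 25% threshold; that is not supported, since 17 of 72 assumed pairs reach it, and none of the 24 pairs with a single small difference does.

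Where baseline and follow-up come from the same local laboratory, little is lost. Where they do not, one subject can be misclassified at a visit, worth about 11 points in a group of 9 or 33 in a group of 3. The failure to preserve ULN multiples follows from the formula whenever the ratio of lower to upper limit differs between laboratories, for any value other than the ULN itself.

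**What to change.** In SAP 7.2:
- Apply unit conversion only to serum creatinine, and calculate eGFR from that value.
- Classify ALT, AST, ALP and bilirubin as multiples of the reporting laboratory's own ULN.
- Keep the formula, if wanted, only for descriptive summaries of other analytes.

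In SAP 6.2, state that unrescaled creatinine is used for the stability and change endpoints. If any local values occur, repeat the two stability tables without them.

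The cost is a few sentences, a local-laboratory flag in the analysis dataset and, only if needed, two extra tables. With creatinine in common units the rescaling error is zero at every level. The downside is that true between-laboratory assay differences stay uncorrected, which the repeated tables would help to show.

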#### 7.2.3. Liver Toxicity

Drug treatment continuation will be evaluated in case of any signs of possible drug-induced hepatic injury as follows:

Drug treatment will be discontinued immediately if either:

 alanine aminotransferase (ALT) or aspartate aminotransferase (AST) is >3× the ULN and (total bilirubin is >2× the ULN or international normalized ratio is >1.5)

or

ALT or AST is >8× the ULN

Drug treatment will be withheld if either:

ALT or AST is >5× the ULN

or

ALT or AST is >3× the ULN with the appearance of fatigue, nausea, vomiting, right upper quadrant pain or tenderness, fever, rash, and/or eosinophilia (>5%)

Drug treatment will be permanently discontinued and the subject withdrawn from the study if the condition persists for more than 2 weeks.

If the subject is not withdrawn from the study, drug treatment may be resumed when both ALT and AST are less than 1.5× ULN.

Any possible hepatic abnormalities will be monitored with repeat testing at a frequency of at least every 72 hours. Frequency of retesting will decrease to weekly or less once abnormalities stabilize. Repeat testing will discontinue once abnormalities are no longer detected.

Causes for the significant liver test abnormalities will be investigated (eg, acute viral hepatitis, Epstein-Barr virus, cytomegalovirus, herpes simplex virus, toxoplasmosis, varicella, and parvovirus), and subjects will be followed up until all abnormalities return to normal or to the baseline state.

Workup will also include consideration of alcoholic and autoimmune hepatitis, hepatobiliary disorders (eg, gallstones), nonalcoholic steatohepatitis, cardiovascular causes (eg, right-sided heart failure), and concomitant medications or supplements.

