13.4. Definition of Analysis Visit Windows

Safety lab, vital sign, and ECG data will be assigned to analysis visit based on windowing (see table below). If more than one assessment (including the early termination or unscheduled assessments) falls within the same defined window, the assessment closest to the target day with non-missing data will be considered for analysis. If two assessment dates are at the same distance from the target day, the first assessment with non-missing data will be considered for analysis.

Study period	Analysis visit	Target day	Analysis window	Interval
Screening	Week -8 to -4	-28	-56 - < -21	NA
	Week -2	-14	-21 - ≤ -1	21
Main Period Controlled Portion	Day 1	1	1	1
	Week 2	14	2 - < 21	19
	Week 4	28	21 - < 42	21
	Week 8	56	42 - < 70	28
	Week 12	84	70 - < 91	21
Main Period Noncontrolled Portion	Week 14	98	91 - < 105	14
	Week 16	112	105 - < 126	21
	Week 20	140	126 - < 154	28
	Week 24	168	154 - < 189	35
	Week 30	210	189 - < 231	42
	Week 36	252	231 - < 273	42
	Week 42	294	273 - < 315	42
	Week 48	336	315 - < 350	35
Follow-up Period (for subjects not entering Part B)	Week 52	364	350 - < 371	21
	Week 54	378	371 - < 385	14
	Week 56	392	385 - < 406	21
	Week 60	420	406 - < 434	28

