13.5. Repeated or Unscheduled Assessments of Safety Parameters

For safety parameters, if a subject has repeated assessments before the start of investigational product, then the results from the final assessment made prior to the start of investigational product will be used as baseline. If end of study assessments are repeated or unscheduled, the last post-baseline assessment will be used as the end of study assessment for generating descriptive statistics. However, all post-baseline assessments will be used for Potentially Clinically Significant (PCS) value determination and all assessments will be presented in the data listings.

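### The by-visit liver table keeps one value per window, so a retest peak can be missing from the SAP's only specified summary of ALT/AST ≥5× ULN, >8× ULN and ≥3× ULN with INR >1.5

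*SAP*

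**What the plan says.** SAP 7.2 defines four liver categories: ALT or AST ≥3× ULN; ≥3× ULN with total bilirubin >2× ULN or INR >1.5; ≥5× ULN; and >8× ULN. On how they are reported it says: "In addition, liver abnormalities will be summarized at each analysis visit including following variables by treatment group and overall". No row for any post-baseline time or for the worst value is specified.

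SAP 13.4 assigns all safety laboratory data to analysis visits by window and gives the selection rule: "If more than one assessment (including the early termination or unscheduled assessments) falls within the same defined window, the assessment closest to the target day" is the one analysed, provided that it is non-missing. Ties go to the earlier result. The size of the value plays no part, and no exception is written for liver tests.

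SAP 13.5 contains a wider rule, under which "all post-baseline assessments will be used for Potentially Clinically Significant (PCS) value determination", and it has all assessments listed. It does not mention the liver categories of SAP 7.2.

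Protocol 7.2.3 sets the retest schedule: "Any possible hepatic abnormalities will be monitored with repeat testing at a frequency of at least every 72 hours". This falls to weekly or less once abnormalities stabilize. The same section ties withholding and discontinuation to thresholds that include "ALT or AST is >5× the ULN" and "ALT or AST is >8× the ULN".

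**The concern.** Retests follow the draw that found the abnormality. If that draw is on or after the target day, every later retest in the window is farther from target and cannot be selected. If enzymes are still rising when first detected, the highest value is then a retest, and the by-visit table does not see it.

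For most laboratory parameters this is an acceptable cost of windowing. Here the categories mirror thresholds on which the protocol acts, and a reader will take the ≥5× and >8× rows as the count of subjects who reached those levels. A report could show zero in the >8× row while its own listing shows a subject above 8× ULN.

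**Working it through.** The plan gives no figure to reproduce. The check has three steps: which categories are covered elsewhere, how many draws compete for one place, and what the rule does to an assumed enzyme course.

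**1. Coverage of each category (SAP 7.2 liver list, SAP Table 1 and the combined row after it, SAP 13.5)**

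| Category | By-visit liver table (one value per window) | PCS (all post-baseline values) |
|---|---|---|
| ALT or AST 3× ULN | ≥3× | >3× |
| 3× with bilirubin >2× ULN | yes | yes, >3× with concurrent bilirubin |
| 3× with INR >1.5 | yes | none |
| 5× ULN | ≥5× | none |
| >8× ULN | yes | none |

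The last three rows rest on the one-value rule alone.

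**2. Draws available after a visit on the target day**

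Inputs: window limits and target days from SAP 13.4; 72-hour (3-day) spacing from Protocol 7.2.3, assumed to continue to the end of the window. Count the days target, target + 3, target + 6 and so on that fall before the upper limit.

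| Window | Target day | Upper limit | Last draw | Draws |
|---|---|---|---|---|
| Week 24 | 168 | <189 | 186 | (186 − 168)/3 + 1 = 7 |
| Week 30 | 210 | <231 | 228 | (228 − 210)/3 + 1 = 7 |
| Week 36 | 252 | <273 | 270 | (270 − 252)/3 + 1 = 7 |
| Week 42 | 294 | <315 | 312 | (312 − 294)/3 + 1 = 7 |
| Week 48 | 336 | <350 | 348 | (348 − 336)/3 + 1 = 5 |

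One of these 5 to 7 values is used. Over all post-Day 1 windows the same count runs from 3 to 7. Retesting that drops to weekly gives fewer.

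**3. Assumed enzyme course**

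The documents give no ALT course, so this one is illustrative (multiples of ULN): Day 210 = 3.5, Day 213 = 6, Day 216 = 9, Day 219 = 7, Day 222 = 4.5, Day 225 = 2.5, Day 228 = 1.4, Day 252 = 1.0.

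- Week 30 window: Day 210 is 0 days from target and Day 213 is 3 days away, so 3.5 is selected.
- Week 36 window: Day 252 is selected, at 1.0.
- Liver table: the subject counts once at ≥3× and never at ≥5× or >8×.
- All post-baseline values: the maximum is 9, so the subject meets ≥3×, ≥5× and >8×.
- PCS table: the subject appears at >3×.

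**4. Range over the visit day**

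Protocol Table 1 allows the Week 30 visit 7 days either side of Day 210. Shift the same course so that it starts on each of the 15 permitted days, 203 to 217:

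| First draw | Value closest to Day 210 | Highest row reached |
|---|---|---|
| Days 203–205 (3 days) | third draw, 9× (Days 209, 210, 211) | >8×, correct |
| Days 206–208 (3 days) | second draw, 6× (Days 209, 210, 211) | ≥5× only |
| Days 209–217 (9 days) | first draw, 3.5× | ≥3× only |

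The peak is recorded or lost according to the timing of the visit. With this course it is graded correctly from 3 of 15 possible visit days.

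**The case against.** The case on the other side is substantial.

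- **Other outputs show the subject.** Someone with a 9× peak would be in the PCS >3× count, in the listing of subjects with a post-baseline PCS value and in the listing of all laboratory values (SAP 7.2). If drug was stopped because of the result, Protocol 11.1.1 calls for an adverse event report, which would normally feed the SAP 7.1 discontinuation tables. SAP 5.1 summarizes the primary reason for discontinuation, and Protocol 7.2.2 lists liver toxicity as a reason. The safety monitoring committee reviews cumulative laboratory data every 4 months.
- **A retest can be selected.** If the visit falls before the target day, later draws move closer to it.
- **The shells are not visible.** SAP 1 and 3.5 place table specifications and layout in a separate document, which may contain an any-time row.
- **No protocol commitment is broken.** Protocol 12.4 asks for laboratory changes by visit and flagged listings. It does not promise a worst-value liver table.

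All of this stands, and it limits the consequence. It does not remove the gap. The adverse event tables are organized by preferred term, not by ULN multiple, and where a diagnosis exists only the diagnosis is reported. In the PCS table a 9× subject and a 3.1× subject look alike. A possible row in unseen shells does not change the rule as the SAP states it.

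A reader might infer three stronger things that the documents do not support. The first is that all the stopping and withholding criteria are counted only under the one-value rule. In fact >3× with bilirubin >2× ULN is a PCS criterion counted on all values, as is the >3× element of the criterion with symptoms. The second is that dividing a 35- to 42-day window by 3 days gives the number of competing draws. That needs retesting from the first day of the window, whereas the mechanism starts at the visit. The third is that a liver case would go unseen or that the hepatic conclusion would change, which the outputs above rule out. It is also the threshold, on whichever sample meets it, that prompts action under Protocol 7.2.3, not the retest as such.

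**Conclusion.** The point holds for three categories: ≥5× ULN, >8× ULN and the INR limb of the combined category. As written, the only specified summary of these uses one value per window, chosen by date, and a peak on a retest can be missing from it.

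The consequence is an understated peak grade in one table. In a trial of up to 12 subjects, one misgraded subject is 1/12 = 8.3% overall, or 1/9 = 11.1% if that subject is in Group 1 with its full 9 subjects.

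This rests on three assumptions: SAP 13.4 governs the liver table, since it covers safety laboratory data without exception; retests run at 72-hour spacing; and the enzyme course in the example is illustrative. Whether such a peak will occur cannot be judged from the documents.

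A side point: SAP 7.2 uses ≥3× and ≥5× in the liver list, while Protocol 7.2.3 and the SAP's own PCS criteria use >3×, and the protocol uses >5×. The passages should be reconciled.

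**What to change.** - In SAP 7.2, add for each liver category the number and percentage of subjects who meet it at any post-baseline time, counted once per subject. Use all scheduled, unscheduled, local and early-termination results.
- Evaluate the combined ALT/AST with bilirubin or INR category on concurrent samples. The PCS row already asks for concurrent bilirubin; the liver list does not, so selecting the closest non-missing result for each test could pair values from different draws.
- In SAP 13.5, name the liver categories alongside PCS in the rule that uses all post-baseline assessments.
- Keep the by-visit table as a supplement.

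The cost is a short addition to SAP 7.2 and 13.5 and one added table shell. No new data are needed, and clinical management is unchanged.
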